3.3 Inclusion Criteria

1. Men, age greater than or equal to 18 years of age.
2. Diagnosis of prostate cancer of any histology.
3. Must meet NCCN guidelines for germline testing (see table below for specific definition of risk groups).
 - a. Men with very low, low or intermediate risk prostate per NCCN guidelines with a positive family history or intraductal histology OR

- Family history here is considered significant if the patient has a first degree relative with prostate cancer or more than one first/second degree relative with prostate cancer.
- ≥3 cancers on same side of family, especially diagnoses ≤50 years of age: bile duct, breast, colorectal, endometrial, gastric, kidney, melanoma, ovarian, pancreatic, prostate (but not clinically localized Grade Group 1), small bowel, or urothelial cancer
- b. Men with high-risk, very-high risk (see Table 3 for NCCN definitions of risk groups), lymph node positive, or metastatic prostate cancer independent of family history of histology.

NCCN definitions of risk groups in localized prostate cancer

Risk group	Clinical/pathologic features			Imaging ^{h,i}	Germline testing
Very low ^f	
 • T1c AND • Grade Group 1 AND • PSA <10 ng/mL AND • Fewer than 3 prostate biopsy fragments/cores positive, ≤50% cancer in each fragment/core^g AND • PSA density <0.15 ng/mL/g 			Not indicated	Recommended if family history positive or intraductal histology See PROS-1
Low ^f	
 • T1-T2a AND • Grade Group 1 AND • PSA <10 ng/mL 			Not indicated	Recommended if family history positive or intraductal histology See PROS-1
Intermediate ^f	Has no high- or very-high-risk features and has one or more intermediate risk factors (IRF):	Favorable intermediate	
 • 1 IRF and • Grade Group 1 or 2 and • <50% biopsy cores positive^g 	
 • Bone imaging^j: not recommended for staging • Pelvic ± abdominal imaging: recommended if nomogram predicts >10% probability of pelvic lymph node involvement • If regional or distant metastases are found, see PROS-9 	Recommended if family history positive or intraductal histology See PROS-1
		Unfavorable intermediate	
 • 2 or 3 IRFs and/or • Grade Group 3 and/or • ≥50% biopsy cores positive^g 	
 • Bone imaging^j: recommended if T2 and PSA >10 ng/mL • Pelvic ± abdominal imaging: recommended if nomogram predicts >10% probability of pelvic lymph node involvement • If regional or distant metastases are found, see PROS-9 	Recommended if family history positive or intraductal histology See PROS-1
High	
 • T3a OR • Grade Group 4 or Grade Group 5 OR • PSA >20 ng/mL 			
 • Bone imaging^j: recommended • Pelvic ± abdominal imaging: recommended if nomogram predicts >10% probability of pelvic lymph node involvement • If regional or distant metastases are found, see PROS-9 	Recommended ^{c,k}
Very high	
 • T3b-T4 OR • Primary Gleason pattern 5 OR • >4 cores with Grade Group 4 or 5 			
 • Bone imaging^j: recommended • Pelvic ± abdominal imaging: recommended if nomogram predicts >10% probability of pelvic lymph node involvement • If regional or distant metastases are found, see PROS-9 	Recommended ^{c,k}

3.4 Exclusion Criteria

Patients are excluded from the study if they:

1. Have had prior germline testing.
2. Have somatic genetic testing that is positive for a possible germline variant.

3.5 Participant Follow-up

Patients will be followed for 24 months following the educational session. We will capture deferred decisions to pursue germline testing during the 24-month follow up period. Data on oncologic outcomes, prostate cancer management, and cancer surveillance will be obtained from the medical record.

4. VARIABLES AND EPIDEMIOLOGICAL MEASUREMENTS

4.1 Exposures

4.1.1 Definition of Primary Exposure

The primary exposure to be tested is an educational session including video on germline testing and review of brochure on germline testing in men with prostate cancer. See attachment.

4.1.2 Definition of Comparison Exposure

The comparison group will include individuals with prostate cancer who meet criteria for germline testing however were not approached about participating in the intervention or were approached and declined participating in the educational intervention. In this context, germline testing education will be at the discretion of the treating medical team.

4.2 Outcomes

Primary Endpoints

1. The proportion of patients who undergo germline testing among those who are enrolled to the study compared to the proportion of patients who undergo germline testing who were eligible, but not enrolled into this study during the study time period
2. Feasibility of implementing an educational intervention for men with prostate cancer at risk of having a hereditary cancer syndrome. This will be assessed by:
 - Accrual rate by month.
 - Proportion of patients who consent to educational intervention among those who are approached (stratified by whether consent was performed in-person or virtually).

Secondary Endpoints

1. Patient understanding of germline testing before and after the education intervention based on questionnaire responses.
2. Patient-reported opinions on germline testing before and after intervention, and patient-reported satisfaction after educational intervention based on questionnaire responses.
3. Physician responses regarding how the germline testing result changed patient management.
4. Prevalence of pathogenic germline mutations among study patients who undergo germline testing.

Exploratory Endpoints

1. Clinical factors (patient and family history, disease characteristics, and outcomes) that are associated with the presence of a germline mutation in a cancer susceptibility gene.

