Outcome(s): Assess the proportion of patients enrolled in the study who underwent germline testing to the proportion of patients who did not enroll in the study. Assess the effect of a patient educational program on increasing germline genetic testing rate among adult prostate cancer patients who are recommended to receive germline testing per NCCN guidelines. .

Sample Size Estimations: Target accrual is 50 patients in 12 months.

Statistical Analysis: For the primary endpoints of feasibility of implementing an educational intervention, this will be assessed by the accrual rate over 12 months. For the endpoint of efficacy of the intervention in improving rates of germline testing, the proportion of patients who undergo germline testing in this study will be compared to the proportion of patients who undergo germline testing who were eligible, but not enrolled into this study during the study time period.

AMENDMENT HISTORY

Date	Section of study protocol	Amendment or update	Reason
		N/A	

MILESTONES

Milestone	Planned date
Finalize survey instruments	July 2021
Finalize Redcap database along with CRFs	August 2021
Hiring of clinical research coordinator	August 2021
Completion of video	September 2021
Training of research coordinator	August- September 2021
Start of accrual	October 2021
6-month assessment of accrual	April 2022
Database lock	October 2022 (or sooner if 50 patients are accrued)
Analysis	November 2022
ASCO Abstract	January 2023
First Manuscript	March 2023

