3. METHODOLOGY

3.1 Study Design – General Aspects

We will then screen genitourinary oncology clinics at UC San Diego Health System to identify patients who are eligible for germline testing. After approval from their treating physician, we will approach patients in the clinic and introduce the educational intervention, which will consist of a one-on-one in-person educational sessions reviewing the rationale and the risks and benefits of germline testing. A virtual educational session was added due to the COVID-19 pandemic and will ideally occur over the Epic video chat platform, Doximity video chat, but can also occur via telephone for patients who are unable to use video chat.

The educational intervention will occur with a clinical research coordinator who will be trained to educate on germline testing in prostate cancer. At the start of the session, the patient will be given a short questionnaire (Appendix A) to assess their understanding about germline and genetic testing, along with a Family History questionnaire (Appendix B). Following this, the session will then include a one-on-one review of an educational handout on germline testing in prostate cancer (Appendix E). The handout will provide a concise, yet comprehensive review of germline testing including:

1. Overview of genetic germline testing
2. Rationale for germline testing in prostate cancer
3. Implications of germline testing in terms of patient's clinical care
4. Implications to family
5. Overview of results including discussion of pathogenic germline mutation and variants of unknown significance
6. Discussion of benefits and risks of testing

Session Overview	
Time (approximately)	Objective
1-5 minutes	Introduction
10 minutes	Pre-intervention survey
5 minutes	Video
10 minutes	Review of brochure
5 minutes	Time for patient to ask questions
10 minutes	Post-intervention survey

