3.2 Study Population

The target population for this study is patients older than 18, with prostate cancer who meet the NCCN criteria for germline testing and who have not undergone prior germline testing.

Subjects will include those patients seen at a facility in the UCSD Health System. Genitourinary oncology clinics will be screened 1 week in advanced for eligible patients. Recruitment procedures will also involve the review of subject records by designated study personnel (e.g., investigators and/or study coordinators) in order to identify potentially eligible subjects. Since Protected Health Information (PHI) will be accessed via the hospital's medical record database and scheduling system (e.g., EPIC/IDX) *prior* to contacting the potential subject about the research study, we have been granted a partial waiver of HIPAA authorization for access to PHI for purposes of prescreening only.

For patients who are eligible for the trial, the investigator will approach the subject and offer participation in the trial. Standard HIPAA authorization to collect research data from the subject's medical record will be obtained at the time of informed consent. Given the COVID-19 pandemic, we are conducting sessions both in clinic and virtually. This will primarily occur via video chat or telephone. Given that this is a low-risk intervention of an educational session, we believe that virtual consenting is also appropriate here given the current pandemic.

For patients who decline the intervention or have not been approached at the time of analysis, these patients will be considered a separate cohort for comparison to the intervention cohort.

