1. The (pre-screening) research involves no more than minimal risk to the subjects as the only risk is loss of confidentiality and all reasonable measures to protect confidentiality will be carried out;
2. The waiver will not adversely affect the rights and welfare of the subjects used as the only risk is loss of confidentiality and all reasonable measures to protect confidentiality will be carried out;
3. The (pre-screening) research could not practicably be carried out without the as the research staff needs to search the EPIC electronic database to identify eligible subjects; and
4. Whenever appropriate, the subjects will be provided with additional pertinent information after participation.

Informed Consent:

Individuals who fulfill the eligibility criteria will be offered participation in this study. The patient's treating physician will authorize the investigator or study coordinator to meet with the patient. Consent may occur in-person, via video chat, or via telephone. Study candidates will be asked to provide written consent, using an IRB-approved informed consent form. The investigator or study coordinator will describe the study to potential participants. The investigator or study coordinator will provide potential participants with a blank informed consent form. The individual will be given ample time to read this consent form at the same visit or may take it with them to read at another time. The study candidate will be given the opportunity to ask and receive answers to all questions they may have about the study, its risks and benefits, and the consent form itself before signing the consent form. As this research is subject to HIPAA Privacy Rule provisions, study candidates will also be requested to sign a separate HIPAA authorization form specific to the research study for the use of PHI. The consent process will be appropriately documented.

Survey Administration:

All surveys will be available as secure links sent to the participant's provided email through REDCap. The patients can also opt to complete the surveys by phone with the research assistant or on paper.

Family History Questionnaire: The Family History Questionnaire (FHQ) is the standard method of self-reported data collection for patients at in the Genitourinary Program at UCSD. This has been modeled from Family History Questionnaires utilized within our Cancer Genetics Program at UCSD and others across the country but modeled for men with prostate cancer.

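### Primary Endpoint 2 stratifies the consent proportion by how consent was performed, which is not defined for every man who declines and can shift among men who consent, so the in-person and virtual proportions are ambiguous and open to bias.

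*Combined protocol and SAP*

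**What the plan says.** Section 4.2 gives two measures of feasibility: accrual by month, and the "Proportion of patients who consent to educational intervention among those who are approached (stratified by whether consent was performed in-person or virtually").

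The passages that decide how a man could be placed in a stratum are these:

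- **Approach.** Section 3.1 says "we will approach patients in the clinic and introduce the educational intervention".
- **Virtual consent.** Section 3.2 adds that "we believe that virtual consenting is also appropriate here given the current pandemic".
- **Mode and timing of consent.** Section 5.1.2 (Informed Consent) says "Consent may occur in-person, via video chat, or via telephone", and that a candidate given the form "may take it with them to read at another time".
- **Recording.** Section 5.1.2 says only "The consent process will be appropriately documented". The variable list in 4.3 has no item for mode of approach or mode of consent.
- **Men who decline.** Section 3.2 says "For patients who decline the intervention or have not been approached at the time of analysis, these patients will be considered a separate cohort". They are pooled with men never approached, and no mode is assigned to them.

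The synopsis describes the feasibility assessment more narrowly: "this will be assessed by the accrual rate over 12 months". Section 4.5.1 has no analysis specific to the consent proportion, although its general statement on exact confidence intervals would cover it.

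**The concern.** A stratified proportion needs a stratifier that is known for every member of the denominator and is fixed before the outcome. The mode in which consent was performed falls short on both counts.

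First, it is not defined for a man who says no at first approach, before any consent discussion. He belongs in the denominator, but the plan does not say in which stratum.

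Second, it can be set after approach. A man approached in clinic who takes the form home and consents by telephone has a consent mode that differs from his approach mode. A man approached beside him who declines on the spot has nothing to move him out of the in-person group. The stratifier is then partly a result of the outcome it is meant to divide.

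At stake is the only comparison of in-person with virtual among the endpoints in 4.2. Sections 4.6.1 and 4.6.3 also count on virtual options to limit recruitment bias, so readers are likely to look at this breakdown.

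**Working it through.** **The plan's own figure.** The documents state no figure for the consent proportion. Their only precision statement (4.5.1 and 4.8) concerns the germline-testing proportion: a width of 0.27 to 0.29 with 50 patients. The exact method reproduces it: 0.2675 at an observed proportion of 0.3 or 0.7, 0.2841 at 0.4 or 0.6, and 0.2895 at 0.5. This point does not touch it.

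**How many men lack a completed consent.** Target accrual is 50 (synopsis). The documents give neither the number approached nor the consent rate, so the rate is assumed. Approached = 50 / rate; declining = approached − 50.

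| Assumed consent rate | Approached | Declining |
|---|---|---|
| 50% | 100 | 50 |
| 60% | about 83 | about 33 |
| 70% | about 71 | about 21 |
| 80% | 62.5 | 12 or 13 |

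Over this range, roughly 12 to 50 men have no completed consent from which to read a mode.

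**Effect of a mode that shifts among consenters.** Let A be the number approached in clinic, B the number approached remotely, p the true consent rate (the same in both), and s the number of clinic consenters who sign remotely.

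By mode of approach: in-person = pA/A = p; virtual = pB/B = p.

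Consenters placed by consent mode, decliners by the mode in which they were approached:

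- in-person = (pA − s) / (A − s)
- virtual = (pB + s) / (B + s)

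With p below 1 and s above 0, the first is below p and the second above it, so virtual looks better although nothing differs. The reverse flow (remote approach, signing in clinic) would push the other way. Because 3.1 describes approach in the clinic, the first direction is the more likely.

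| Assumed A, B, p, s | By approach | In-person | Virtual | False gap |
|---|---|---|---|---|
| 60, 40, 50%, 0 | 50% and 50% | 30/60 = 50% | 20/40 = 50% | 0 |
| 60, 40, 50%, 5 | 50% and 50% | 25/55 = 45% | 25/45 = 56% | about 10 points |
| 60, 40, 50%, 10 | 50% and 50% | 20/50 = 40% | 30/50 = 60% | 20 points |
| 80, 20, 50%, 15 | 50% and 50% | 25/65 = 38% | 25/35 = 71% | 33 points |

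**What does not move.** In every row the overall proportion is 50/100 = 50%. The number accrued is 50 whichever coding is used.

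**The case against.** The strongest reply is that consent in 5.1.2 is a process: the study is described, a form is handed over, questions are answered, and the process is documented. On that reading a man who declines in or after the discussion does have a mode, namely the one in which the discussion was held. This stands in part, and it is why one cannot say that men who decline never have a mode. But the protocol does not adopt this reading, and it gives no mode to a man who declines before any discussion. It also still sends clinic-approached later signers to the virtual stratum while men who decline in clinic stay in-person. Placing a man who later declines by telephone in the virtual stratum would soften the bias, but the plan does not say to do that either.

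A reader might infer that the rule makes every stratum 100% by construction. It does not. The endpoint is a proportion among those approached, so men who decline stay in the denominator; what is missing is their stratum.

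A reader might also infer that the plan loses its test of whether virtual delivery works. The documents do not support this. The stratifier concerns consent, not the educational session; no objective or hypothesis in section 2 compares modes; and 4.5.1 plans no test between them.

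Two further replies are fair. The switching counts are assumed, and the plan prescribes no mixed coding; the arithmetic shows what the wording permits, not what will happen. And the case report forms are not shown, so the absence of a field in 4.3 does not prove that approach mode goes unrecorded.

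**Conclusion.** The point holds for the stratified breakdown only. As worded, the in-person and virtual consent proportions cannot be computed without a rule the plan does not state, and the natural ways of supplying one let the stratum depend on the outcome. Two analysts could report different results from the same data.

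The size depends on how many clinic-approached men sign remotely, which the documents do not give. With a true rate of 50% in both modes, the false gap runs from 0 with no switching, to 20 points (40% v 60%) with 10 of 30 clinic consenters switching, to 33 points in the more extreme example.

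It would be wrong to conclude that the primary feasibility result fails. The overall consent proportion and monthly accrual do not use the stratifier. Hypothesis 1 in section 2.1 and the synopsis judge feasibility by recruitment to target and by accrual. This should be corrected because the breakdown sits within a primary endpoint and because approach mode for men who decline may be unrecoverable if it is not noted at the time.

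**What to change.** In 4.2, replace the stratifier with: *stratified by mode of first approach (in-person or virtual)*. Record that mode at the time of approach for every man approached, including those who decline. Report the mode in which consent was signed only as a description of the men who consented.

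The cost is one phrase in 4.2 and one recorded field. It needs no extra patients or procedures and leaves the sample size unchanged.

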2.3 Exploratory Objective(s) & Hypotheses

Objectives

- (1) To describe the demographic and clinical characteristics among all patients who received germline testing and subsequently, stratify by presence of germline mutations in cancer susceptibility genes.

Hypotheses

- (1) We hypothesize that patients with pathogenic germline alteration have more aggressive disease patterns in both the localized and advanced settings.

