4.3 Other Variables and Covariates

We will capture the following additional demographic, clinical, and disease variables:

- Demographic data: Age, Marital Status, Race, Ethnicity, Employment Status, Clinician, Primary Language, Country of Birth, Education Level.
- Previous medical history: Comorbidities, Smoking History, and Family History of Malignancies.
- Disease characteristics: Date of Diagnosis, Site of Disease, Site(s) of Metastasis, if applicable, Histology/Grade/Pathologic Parameters, PSA, Stage, Somatic Molecular Profile, Date of Collection of Tissue Analyzed, Type of Tissue Analyzed.
- Treatment data: Date of Surgery, Date of Radiation, Dose of Radiation, Systemic Therapy.
- Treatment outcomes data: Toxicity, Dose Reduction, Reason for Dose Reduction, Response, Progression, Survival.

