4.4 Statistical Analysis Plan

4.5 Statistical Methods – General Aspects

4.5.1 Primary Objective(s): Calculation of Epidemiological Measure(s) of Interest (e.g. descriptive statistics, hazard ratios, incidence rates, test/retest reliability)

Primary Endpoints

With regards to the primary endpoint, at the completion of the study, the proportion of patients who complete germline testing among all who are enrolled to the study will be computed. A sample size of 50 patients produces a two-sided 95% confidence interval on the proportion with a width ranging from 0.27 to 0.29 when the observed proportion ranging from 0.3 to 0.7. For proportions, 95% confidence intervals will be calculated using the exact method.

We will also compute the proportion of patients who completed germline testing for all eligible prostate cancer patients evaluated in clinic but not enrolled into this study during the study period. Characteristics between these two groups will be compared using Fisher's Exacts or Wilcoxon Rank Sum tests. The proportion of patients who underwent germline testing in the intervention vs non-intervention cohorts will be compared using Fisher's exact test.

4.5.2 Secondary Objective(s): Calculation of Epidemiological Measure(s) of Interest (e.g. hazard ratios, incidence rates, test/retest reliability)

Secondary endpoints including germline mutation frequency, patient understanding of germline testing, and medical management from germline testing will be described using descriptive statistics such as bar graphs, box plots, percentages, means and standard deviations, etc.

4.5.3 Exploratory Objective(s): Calculation of Epidemiological Measure(s) of Interest (e.g. hazard ratios, incidence rates, test/retest reliability)

- Associations between clinical factors and pathogenic germline alterations will be evaluated using Odds Ratio.
- Impact of germline testing on prostate cancer and cancer surveillance management will be qualitatively described.

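### Section 4.5.3 leaves progression and survival to a yes/no odds ratio by carrier status, with no time origin, censoring rule or data cut, although follow-up at the listed lock is only about 0 to 12 months

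*Combined protocol and SAP*

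**What the plan says.** Section 4.2 gives the exploratory endpoint as "Clinical factors (patient and family history, disease characteristics, and outcomes) that are associated with the presence of a germline mutation", so outcomes count as clinical factors. Section 4.3 says which outcomes are captured: "Treatment outcomes data: Toxicity, Dose Reduction, Reason for Dose Reduction, Response, Progression, Survival". Section 4.5.3 gives one method for the associations: "Associations between clinical factors and pathogenic germline alterations will be evaluated using Odds Ratio". Its only other item is a qualitative description of how testing affected management. Hazard ratios appear only as an example inside the section titles. No section sets a time origin, a censoring rule, a landmark time or a data cut for outcomes.

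The hypothesis these data would inform is in section 2.3: "We hypothesize that patients with pathogenic germline alteration have more aggressive disease patterns in both the localized and advanced settings".

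On follow-up, section 3.5 says "Patients will be followed for 24 months following the educational session", with outcomes taken from the medical record and no assessment schedule. It adds: "We will capture deferred decisions to pursue germline testing during the 24-month follow up period". The milestones table starts accrual in October 2021, locks the database in October 2022 or sooner if 50 patients are accrued, and schedules the analysis for November 2022.

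**The concern.** Progression and death are events in time. The chance that either has been recorded rises with the length of observation. If men have been observed for anything from a few weeks to a year, a two-by-two table of event (yes/no) by carrier status mixes the event rate with the length of observation, and the plan gives the reader no means of separating them.

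At stake is the outcome part of the aggressive-disease hypothesis. Without person-time or curves beside it, an odds ratio above or below 1 cannot be read as faster or slower progression, and its size has no meaning apart from the follow-up pattern at the lock. The primary and secondary endpoints are not affected. Nor is the use of odds ratios for grade, stage, site of disease or family history.

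**Working it through.** **The plan's own figure.** The only stated precision figure is the 95% interval width of 0.27 to 0.29 for a proportion with n = 50 (sections 4.5.1 and 4.8). The exact method gives 0.2675 at an observed 0.3 or 0.7 and 0.2895 at 0.5, so it reproduces. The exploratory analysis has no sample size, event count or power statement to reproduce.

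**Follow-up at the analysis.** October 2021 to October 2022 is 12 months, so follow-up from the session is about 0 to 12 months at lock, and less if the lock is brought forward. The first manuscript is listed for March 2023, 17 months after accrual starts. Even then no man would have 24 months. A common 24-month window is therefore not available to the scheduled analysis.

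**Number of carriers.** Section 1.2 gives a prevalence of 10-12% in advanced disease. That is 5 to 6 carriers if all 50 men are tested, 4 to 4.8 if 40 are tested, and 2.5 to 3 if 25 are tested.

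**Assumption.** The documents give no event rate. I use a constant hazard h = 0.05 per month, the same in carriers and non-carriers unless stated.

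**1. Follow-up unrelated to carrier status.** 40 men, 4 carriers, follow-up uniform on 0-12 months, 0.5 added to each cell, 40,000 simulated trials:

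| Quantity, true hazard ratio 1 | Varying follow-up | Every man at the same average risk (24.8%) |
|---|---|---|
| Median odds ratio | 1.24 | 1.24 |
| SD of log odds ratio | 1.01 | 1.01 |
| Fisher rejection (3,000 runs) | 1.9% | 2.1% |

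Varying follow-up adds neither bias nor variance. The median of 1.24 appears in both columns and comes from the small cells.

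**2. What is lost.** In the same trials the log odds ratio correlates 0.29 with the carrier minus non-carrier difference in mean follow-up (0.29² is about 8% of its variance). At a true hazard ratio of 3 the correlation is 0.43. The log rate ratio per person-month (0.5 added to event counts) has an SD of 0.90 against 1.01 at a hazard ratio of 1, and 0.81 against 1.06 at a hazard ratio of 3. The two measures share a null value but not a scale away from it, so the second comparison is only indicative.

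**3. Dependence on follow-up, equal in both groups.** With risk 1 − exp(−ht) and a hazard ratio of 2, the odds ratio is (e^(2ht) − 1)/(e^(ht) − 1) = e^(ht) + 1. At h = 0.05 this is e^0.3 + 1 = 2.35 at 6 months, e^0.6 + 1 = 2.82 at 12 months and e^1.2 + 1 = 4.32 at 24 months. One hazard ratio gives three odds ratios.

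**4. A systematic difference in follow-up (illustration only).** Mean risk over uniform follow-up from a to b is 1 − (e^(−ha) − e^(−hb))/(h(b − a)). With equal hazards:

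| Carriers | Non-carriers | Risks | Odds ratio |
|---|---|---|---|
| 0-8 months | 4-12 months | 17.6% v 32.5% | 0.44 |
| 0-10 months | 2-12 months | 21.3% v 28.8% | 0.67 |
| 0-12 months | 0-12 months | 24.8% v 24.8% | 1.00 |

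Nothing in the documents says that carriers enter earlier or later than other men.

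**The case against.** The strongest reply is that chance imbalance does no harm here. With few carriers, mean follow-up will often differ between the groups: the ratio falls outside 0.75-1.33 in about 36% of trials with 4 carriers. A reader might infer that the odds ratio is then biased, so that the result shows follow-up instead of biology. The documents do not support that. If follow-up is unrelated to carrier status, every man has the same marginal risk under equal hazards, and the imbalance is already part of ordinary sampling error, as step 1 shows. Nor may the 36% be joined to the 0.44. That example needs a mean ratio of 0.5, and an imbalance that large in either direction occurs in about 4.5% of trials.

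A reader might also infer bias from deferred testers, who must survive until they are tested. Carriers and non-carriers meet the same condition before status is known, and nothing in the plan suggests that carriers defer more often. No differential bias follows.

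Two further replies have weight. No single sentence says that progression or survival will be coded yes/no. That follows from reading 4.2, 4.3 and 4.5.3 together, and toxicity, dose reduction and response, also listed in 4.3, suit an odds ratio. And the data will be thin under any method: with 4 carriers about one carrier event is expected (4 × 24.8% = 0.99), and none occurs in 32% of trials. A hazard ratio of 2 with 12% carriers would need 155 events for 80% power.

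What remains is that the plan gives no other method for progression and survival, and that the 24-month follow-up which would equalise observation is not reached by the listed lock.

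**Conclusion.** The point holds as a minor one about method and reporting. As written, progression and survival fall under an odds ratio with no origin, censoring or cut, at a lock where follow-up is about 0 to 12 months. The cost is lost time information (log-scale SD 1.01 against 0.90 in the case examined) and an estimate that cannot be interpreted without the follow-up pattern. The plan would also have no protection if follow-up did differ by carrier status. It is not evidence of bias: with follow-up unrelated to carrier status there is no systematic distortion and no excess of false positives.

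The sizes rest on an assumed constant hazard of 0.05 per month, uniform entry, 40 tested men and 4 carriers. The 0.44 and 0.67 illustrate a systematic difference in follow-up and are not expected values. The reading assumes that the outcomes in 4.2 are those listed in 4.3.

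**What to change.** In section 4.5.3:

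- Keep the odds ratio for factors fixed at entry (family history, grade, stage, site of disease) and for outcomes that are not time-dependent.
- For progression and survival, set the time origin at collection of the germline sample, state the data cut, and censor at last chart contact. This origin also leaves a deferred tester's waiting time out of the count.
- Report events per person-month and Kaplan-Meier curves by carrier status. Give an exploratory hazard ratio with its confidence interval only if there are enough events.

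Reconcile section 3.5 with the milestones: either say that these outcomes are analysed with whatever follow-up exists at the October 2022 lock, or schedule a later cut for them.

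The cost is a few sentences, and dates that the planned chart review should already yield. The drawback is that with about 3 to 6 carriers the estimates will be very imprecise whatever the method, and some hazard ratios may not be estimable. The plan should say so in advance.
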